# Relationship Between Acute Phase Markers and Post-operative Pain in Laparoscopic Cholecystectomy: An Observational Study

March 3, 2023

**Background:** Many patients undergoing laparoscopic cholecystectomy are prone to developing acute and chronic post-operative pain.

The aim of the study is to show a possible correlation between pain and acute phase proteins in order to:

- predict the severity of pain;
- select most suitable pain relief therapy for the patient.

**Materials and methods:** The day after surgery, some serum markers are determined by a blood sample. The markers analyzed are:

- Leukocytes;
- C-reactive protein (CRP);
- D-dimer;
- Fibrinogen;
- Neutrophil-to-Lymphocyte Ratio (NLR).

Pain level is assessed using the NRS scale at different times:

- 1st post-operative day;
- 7th post-operative day;
- One month after surgery;
- Three months after surgery;
- Six months after surgery.

Other data collected for the study are: gender, age and BMI.

**SAP:** Statistical Analysis Plan was expressed as percentages, median, and range of values. Differences between continuous variables were analyzed with the Mann-Whitney U test, whereas differences between categorical variables were evaluated with the chi-square or the Fisher's exact test, when appropriate. Variables achieving statistical significance ( $P<0.05$ ) at univariate analysis were entered in a backward multivariate logistic regression model, removing the variable if  $P$  more than 0.10.  $P$  less than 0.05 was considered statistically significant. Statistical analysis was carried out with the SPSS software packaging (SPSS Inc., Chicago, IL), version 13.

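### Prediction of pain is a stated purpose, but every decision rule in the SAP is a P value and no measure of predictive accuracy is planned

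*Combined protocol and SAP*

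**What the plan says.** The document is a short combined protocol and SAP. Its Background paragraph sets out to demonstrate a possible correlation between pain and acute phase proteins, and gives two purposes for it: to "predict the severity of pain" and to "select most suitable pain relief therapy for the patient". Five markers are measured in blood on the day after surgery. Materials and methods adds that "Pain level is assessed using the NRS scale at different times", namely day 1, day 7, and one, three and six months.

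The SAP paragraph then lists the whole analysis:

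- Summaries are "expressed as percentages, median, and range of values".
- "Differences between continuous variables were analyzed with the Mann-Whitney U test", and categorical variables are compared by chi-square or Fisher's exact test.
- "Variables achieving statistical significance" at P<0.05 in the univariate step are "entered in a backward multivariate logistic regression model, removing the variable if" P exceeds 0.10.
- In general, P "less than 0.05 was considered statistically significant".

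Nothing else is planned. The remainder of the document is a reference list.

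**The concern.** Both purposes concern the individual patient: how much pain this person will have, and which pain relief suits this person. Whether a marker can serve them depends on how well it separates patients with more pain from those with less, and on whether predicted risks agree with observed ones. A P value answers a different question, namely whether the marker's distribution differs between groups by more than chance would readily explain. For a fixed P value, the separation it implies shrinks as the sample grows.

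The SAP has no quantity that bears on separation or agreement. The logistic model is used to retain variables by P value; the plan does not specify odds ratios with intervals, still less a measure of model performance. At stake is the interpretation of the result. A significant marker could be presented as a predictor, and as a basis for choosing pain relief, with no estimate of how often it would classify a patient wrongly.

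**Working it through.** **1. Purposes and planned outputs side by side.**

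| Stated purpose or step | What the SAP provides |
|---|---|
| Correlation of markers with pain | Mann-Whitney, chi-square or Fisher test |
| Prediction of severity | Backward logistic model, with variables kept or dropped on P values |
| Choice of pain relief | No analysis |
| Accuracy (AUC, concordance, sensitivity, specificity, calibration) | None |
| Optimism correction or validation | None |

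The three numerical rules (entry P<0.05, removal P>0.10, significance P<0.05) are all P-value rules.

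**2. How weak can a significant marker be?** The plan states no sample size, event rate or effect size, so it has no figure of its own to reproduce. The Mann-Whitney statistic divided by n1 × n0 is the AUC, so the significance limit converts directly into an AUC:

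AUC_min = 0.5 + 1.96 × √[(n1 + n0 + 1) / (12 × n1 × n0)]

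Here n1 and n0 are the numbers with high and lower pain.

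- From the document: the Mann-Whitney test and the 0.05 level.
- Assumed: a two-sided test, two groups formed by splitting the NRS, no ties, the normal approximation, total n, and the share with high pain.

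Example, n=200 with 30% high pain (60 and 140): 201 / (12 × 60 × 140) = 201 / 100,800 = 0.001994. The square root is 0.04466; times 1.96 gives 0.0875. AUC_min = 0.588.

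| n | 20% high pain | 30% | 50% |
|---|---|---|---|
| 50 | 0.702 | 0.676 | 0.662 |
| 100 | 0.642 | 0.624 | 0.614 |
| 200 | 0.600 | 0.588 | 0.580 |
| 300 | 0.582 | 0.571 | 0.565 |
| 500 | 0.563 | 0.555 | 0.551 |

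**3. Reading these AUCs.** Under an equal-variance binormal model, the standardised difference is d = √2 × Φ⁻¹(AUC), and the point where sensitivity equals specificity is Φ(d/2). With 30% high pain, the limits correspond to about 63% each at n=50 (d=0.65), 59% at n=100 (d=0.45) and 56% at n=200 (d=0.31). A coin toss gives 50%. This is only an aid to reading the AUC; the plan proposes no cut-off.

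**4. How often would a weak marker pass?** The values above are the smallest observed AUCs that reach significance, not expected ones. For a marker whose true AUC is 0.60, simulation (2,000 runs per sample size, normal markers, 30% high pain) gives P<0.05 in about 36% of studies at n=100, 62% at n=200, 79% at n=300 and 96% at n=500. A weak marker may therefore pass, and the chance rises with n.

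**The case against.** The strongest reply is that the main clause of the aim is about correlation, in a study titled as an observational study of a relationship. Prediction and choice of therapy are purposes that the correlation is meant to serve, and tests of association are a recognisable first step. This stands in part: the planned tests suit the main clause. It does not remove the gap, because prediction is a named purpose and nothing planned informs it. If association is all that is intended, the wording of purpose and conclusion should say so.

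A reader might infer more than the documents support, in three ways.

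- *A significant marker will be declared predictive.* The SAP never says so. It says what counts as statistically significant and states no conclusion to be drawn from that. The step from significant to predictive is an inference from the stated purposes, so the risk is that it could happen.
- *Any marker that passes must be nearly useless.* This depends on n. At n=50 the limit is 0.66-0.70, where describing the marker as one that barely separates patients is less apt.
- *The plan will produce over-optimistic cut-offs.* No cut-off or ROC curve is planned, so that bias cannot be charged to the plan. It matters only for how an accuracy figure, if added, should be computed.

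It can also be said that an AUC could be calculated later. It could, but it would then be a post hoc figure on data already used for screening and selection, without a pre-specified outcome or correction.

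**Conclusion.** The concern holds as a mismatch between purpose and analysis. Carried out exactly as written, the plan can show that a marker is associated with pain; it cannot show whether the marker predicts pain in a patient. A weakly discriminating marker could then be reported as predictive.

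The size is conditional. Over an assumed 20-50% with high pain, significance is reached at an observed AUC of about 0.66-0.70 at n=50, falling to 0.57-0.58 at n=300. The sample size, the high-pain share and the two-group split of the NRS are assumptions, since the documents give none of them. The absence of any accuracy measure does not rest on these assumptions. The change is worth making because it costs little and bears directly on the study's own purpose.

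**What to change.** Take one of two routes.

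**Keep prediction as a purpose.** Add to the SAP:

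- one pre-specified NRS outcome and time point for the accuracy analysis;
- for each marker and for the final model, the AUC with 95% CI or, if the NRS is not to be dichotomised, a rank concordance with NRS and its 95% CI;
- for the final model, a bootstrap optimism correction that repeats the univariate screening and the backward selection in every resample, because accuracy measured on the patients used to choose the variables tends to be too high;
- a rule such as: *a marker will be described as predictive only on the basis of its accuracy and confidence interval (for the model, corrected for optimism), and not on P<0.05.*

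**Or restrict the claim.** State that the conclusions concern association only, and that prediction and choice of pain relief are left to later work.

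**Cost.** No further patients, visits or samples are needed. The per-marker AUC is a rescaling of the Mann-Whitney statistic already planned. The first route is more than a change of wording, however: the NRS outcome must be defined first, and a logistic model in any case needs a binary one. The bootstrap may need software beyond the SPSS version 13 named in the SAP. Reported accuracy will look less favourable than an uncorrected figure. The second route costs only rewording.
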